Phase II of TOHP will go beyond the aforementioned trials by providing convincing answers to the three most important clinical questions related to non-pharmacologic therapy in people with high normal BP: Can DBP and SBP be lowered and a substantial proportion of new cases of hypertension be prevented by weight loss or sodium restriction? If so, which of the interventions (combined weight loss and sodium restriction, weight loss alone, or sodium restriction alone) is effective? Whether the combination of weight loss and sodium restriction is more effective than intervention with either weight loss or sodium restriction alone is an important and unresolved question. Within the context of the available power, Phase II of TOHP will provide additional information regarding this issue. Finally, TOHP II will provide an opportunity to test whether the benefits of a non-pharmacologic intervention can be maintained over a prolonged period of follow-up. A positive result will provide valuable information on the need for a shift in public policy and clinical practice from our current virtually exclusive "high risk" hypertension detection and treatment approach to one in which primary prevention of hypertension and the high risk approach are both emphasized. The latter represents the only long-term solution to our epidemic of BPrelated cardiovascular disease.

STUDY DESIGN

The study design for Phase II is based on the preliminary findings from Phase

[figure not shown]
I of TOHP and is the result of discussions among all the Principal Investigators, NHLBI representatives, and the Coordinating Center. The major concerns in the development of the design have been to meet the scientific aims of the study in the most effective and efficient manner possible.

The study design is a 2 x 2 factorial of weight loss and sodium restriction. Participants will be randomly assigned to one of four possible groups: weight loss alone (Wt), sodium restriction alone (Na), combined weight loss and sodium restriction (WtNa), or a usual care control group (usual care).

Men and Women

30-54 years of age

Body mass index: men - $_{\geq}26.1$ - $_{\leq}37.3$ kg/m 2 ; women - $_{>}24.4$ - $_{<}37.3$ kg/m 2

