This design allows us to test the overall effect of weight loss and the overall effect of sodium restriction. The effect of the combined intervention can also be tested. In addition, we will examine the effect of the combined intervention as compared to weight loss, sodium restriction and the absence of weight loss and sodium restriction.

All nine clinics will randomize participants into all four arms and subjects will be distributed equally among the three treatment groups and the control

group (1/4 each). Randomization will be stratified by clinic to insure even distributions into the four treatment groups at each of the clinical centers.

SAMPLE SIZE AND POWER

- A. The hypotheses to be tested in this factorial design are 1) the overall effect of weight loss (i.e., groups A and B vs. groups C and D); 2) the overall effect of sodium restriction (i.e., groups A and C vs. groups B and D); and 3) the effect of the combined intervention (i.e., group A vs. group D). The primary endpoint for testing these hypotheses will be change in mean diastolic blood pressure (DBP) both from baseline to termination BP and from baseline to the average of all DBP's from 6 months to 36 months. The assumptions for calculating the necessary sample size for these continuous endpoints are as follows:
 - 1. Baseline blood pressure measurements will be taken at 3 visits with three measurements per visit. Follow-up BP measurements will be taken over 3 visits at 18 and 36 months, and 1 visit at 6, 12, 24 and 30 months, each with 3 measurements per visit. The termination BP is defined as the BP at 36 months or before starting BP medication, which will also be based on 3 visits with 3 measurements per visit. The blood pressure measure for an individual is thus an average of nine readings at baseline and at termination. The variance of the change from baseline (x_1) to termination (x_2) can be written as:

$$\sigma_1^2 = V(x_2 - x_1) = 2\sigma_p^2(1 - \rho_{0,36}) + 2(\sigma_A^2 + \sigma_e^2/k)/n$$

where σ_{p}^{2} = between-person variance

 σ_{λ}^{2} = between-visit variance

 $\sigma_{\rm e}^2$ = within-visit variance

n = number of visits = 3

k = number of measurements per visit = 3

 $\rho_{\text{i,j}}$ = tracking correlation of the individual's true blood $pressure\ mean\ from\ time\ i\ to\ time\ j,\ with\ 0\ representing$ baseline

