Using the assumptions for change from baseline to termination a sample size of 621 per group or a total of 2484 is needed to achieve 80% power for all three hypotheses. With the proposed sample size of 2250 we thus do not achieve 80% power to detect a difference of 1.5 mmHg between the combined intervention and the placebo with this endpoint. We do, however, have more than adequate power to address the main hypotheses of weight loss and sodium restriction. The power for each hypothesis for various differences in DBP change from baseline to termination is shown in Table 1. As indicated, with 80% power, we can detect an effect of 1.2 mmHg for overall weight loss or sodium restriction or a difference of 1.6 mmHg between the combined intervention and placebo groups. The last column of Table 1 reflects

12/15/1992

Table 1 Power (%) for a primary hypothesis with a total sample size of 2250 using DBP change from baseline to termination.

Difference in DBP change	Overall effect of weight loss or sodium restriction	Combined vs. control *
1.0	69.5	36.6
1.1	78.8	44.6
1.2	86.2	52.7
1.3	91.6	60.8
1.4	95.3	68.4
1.5	97.5	75.3
1.6	98.8	81.3
1.7	99.4	86.3
1.8	99.8	90.3
1.9	99.9	93.4
2.0	100.0	95.6

^{*} The power for the combined versus weight loss and for the combined versus Na restriction is the same as that for combined versus control.

the power to test differences between any two groups, including the combined vs. sodium restriction groups and the combined vs. weight loss groups. We thus have 80% power to detect a difference of 1.6 mmHg in the latter two comparisons, which may not be adequate.

The power using DBP change from baseline to the average of all follow-up blood pressures is given in Table 2. The power is greatly increased by using the additional data. We have over 90% power to detect an effect of 1.0 mmHg for overall weight loss or sodium restriction, and almost 80% power to detect a difference of 1.2 mmHg between the combined intervention and placebo group, or either single intervention group.

- B. A secondary endpoint to be considered is the change in systolic blood pressure (SBP) over the course of the trial. Similarly to DBP, the outcomes will be defined as the change from baseline to termination SBP at 36 months or before starting BP medication, and the change from baseline to the average of all SBP's from 6 months to 36 months. The assumptions used for SBP are identical to those for DBP outlined above, with the following parameter estimates:

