Group meetings are the primary mode of contact because groups are efficient from a staffing point of view and also provide social support and facilitate certain aspects of behavioral counseling. Involving spouses and significant

others in intervention meetings while providing samples of low calorie or low sodium food items also facilitates social support.

For the combined intervention, the approach to introducing and integrating sodium topics is based on a review of protocols from other studies in which weight and sodium interventions have been combined successfully (e.g., HIT and TOMHS), as well as the experience of the TOHP Phase II Pilot. Both sodium and calorie content of foods will be addressed simultaneously. Counseling related to food content will be approached from an eating-occasion orientation (i.e., food choices at breakfast, lunch, dinner, social occasions, etc.). Adoption of a regular moderate physical activity program will be emphasized as critical to both weight loss and long term weight maintenance, with exercise opportunities provided in the group meeting.

The purpose of the bi-weekly transition phase of intervention will be to provide a bridge between intensive intervention and the extended intervention phases and to reduce recidivism over the 3 to 4 year follow-up period. The curriculum of these meetings will focus on building relapse prevention skills using the general approach of Marlatt and Gordon (47). Basically, this approach to relapse prevention training includes the following components: identifying high risk situations in which relapse is likely to occur for each participant, teaching participants strategies for minimizing the occurrence of high risk situations, developing alternative active coping strategies for situations which cannot be avoided, and then practicing the selected coping strategies to build confidence and skill. Transition intervention meetings will focus on the full spectrum of intervention goals including adherence to dietary changes, physical activity, and behavioral self-management efforts.

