At the end of the bi-weekly transition phase of intervention, all participants will begin the extended period of intervention. For the weight and weight/sodium intervention groups, biweekly contacts or attendance at minimodules are encouraged for the duration of the trial. For the sodium alone intervention, less frequent monthly contacts and bimonthly meetings are recommended. For efficiency, randomization cohorts will be combined for minimodule group meetings during the extended intervention period, but only within the same intervention (i.e., either Wt, Na or WtNa).

Adherence Enhancement: Several types of strategies will be used to enhance adherence. Items that will help with sodium reduction or weight change will be used as incentives (e.g., coupons for modified foods or samples of these modified foods). Participants will keep daily, then less frequent food records throughout the study. These food records will not be used for data collection. Self-monitoring of food intake provides a framework for planning nutritionally-adequate food substitutions in consultation with the nutrition counselor. In addition, calculating caloric and sodium intake from food records, although subjective and imprecise, helps participants to develop a working knowledge of food content and to keep themselves in the right range for caloric or sodium intake. Participants in weight management intervention are expected to continue self-monitoring their regular physical activity throughout the program.

Weigh-ins at intervention meetings or visits provide objective evidence of weight loss or maintenance. Overnight urine collections will be used to provide objective evidence of adherence to dietary sodium goals. An average from two overnight urine collections will be obtained midway through and at the end of the intensive intervention and periodically during the remainder of

follow-up. This is similar to the successful urine sodium monitoring approach used in Phase I.

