To assess the effects of weight loss, sodium restriction, and their combination, the mean changes in DBP at 36 months in the various groups will be compared. Additionally, the average of all BPs obtained during the trial in the various groups will be compared. The analysis of variance for a two-by-two factorial design will be used to test the main effects of weight loss and of sodium restriction. Multiple regression analyses will be performed to adjust for other covariates, such as age, sex, and initial weight and urinary sodium. To reduce the impact of regression to the mean and to improve the error variance, as well as to adjust for any imbalance, mean initial DBP will also be included in the model. To compare DBP changes in two of the four groups, such as the combined intervention versus placebo, comparisons of means

with a t-test and multiple regression analyses will similarly be used. These methods can also be used to explore the effect of the combined intervention compared to a single intervention such as weight loss alone. More sophisticated methods of longitudinal data analysis such as computing slopes over time or the use of autoregressive models will be used to explore more complex changes in DBP over time in the various treatment groups (48-50).

Because the effect of treatment may not be uniform across all members of a group, we will also examine the distribution of blood pressure changes. Should these appear not to be normally distributed, we will perform nonparametric tests of significance. To examine the effect of actual compliance to the treatment regimen, we will consider change in DBP as a function of actual change in weight and urinary sodium. This is of particular importance because some members of the control group may seek to implement the intervention strategies on their own.

Censoring of this continuous variable due to incidence of hypertension is a potential problem in this analysis. Once antihypertensive medications are prescribed, blood pressure readings become biased in those subjects who should have the highest levels. For this reason we will attempt to acquire and use termination blood pressures obtained prior to initiation of antihypertensive therapy. Furthermore, individuals who are told they are hypertensive may begin some nonmedical intervention; such as weight loss, on their own, perhaps under the advise of their physicians, even if they do not take medications.

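### The active arms are treated in groups and usual care is not, but the planned tests and power tables assume independent participants, so they hold only if outcomes within an intervention group are uncorrelated

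*Protocol*

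**What the plan says.** **Randomisation.** STUDY DESIGN states: "Participants will be randomly assigned to one of four possible groups". It adds that "subjects will be distributed equally among the three treatment groups and the control" group, with stratification by clinic. The unit of randomisation is the person.

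**Delivery.** INTERVENTION METHODS, Counseling Approach, states: "Group meetings are the primary mode of contact because groups are efficient from a staffing point of view and also provide social support". Table 10 gives the same mainly-group contact mode for all three programmes and lists group process and social support among their contents. Wt and WtNa have 14 weekly then 6 biweekly sessions. Na has 10 weekly then 4 monthly sessions. In the extended phase "randomization cohorts will be combined" for mini-modules, but only within the same intervention. No session schedule is described for usual care.

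**Power.** In SAMPLE SIZE AND POWER, section A, the variance of DBP change contains between-person, between-visit and within-visit components only. From this the protocol concludes that, with 80% power, "we can detect an effect of 1.2 mmHg for overall weight loss or sodium restriction", or 1.6 mmHg for combined versus control. The logrank formula in section C has no design effect either.

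**Analysis.** DATA ANALYSES states: "The analysis of variance for a two-by-two factorial design will be used to test the main effects of weight loss" and of sodium restriction. For two-group comparisons it says that comparisons of means "with a t-test and multiple regression analyses will similarly be used". The hypertension endpoints get chi-square, logrank and Cox. The longitudinal and repeated-measures methods mentioned there deal with correlation within a person, not between members of a group.

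**The concern.** This is a partially nested design. Participants who share a group and an interventionist may have correlated outcomes in three arms, while usual-care participants are effectively singletons. Each of the three primary contrasts sets grouped participants against participants who are wholly or partly ungrouped.

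With positive within-group correlation, the true variance of an active-arm mean exceeds the value that the ANOVA or t-test uses. Standard errors are then too small, each test rejects too often under the null, and the printed power does not apply to a valid analysis. A clinic term would not cure this, because the correlation arises within clinic and arm.

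**Working it through.** **Inputs from the protocol.** SD of DBP change is 6.78 (termination). Censoring is Pc = 0.311. The Bonferroni critical value is 2.394 and z_β is 0.84. Total N is 2250, so n = 1125 per side for a main effect and 562.5 for combined versus control.

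**Reproducing the plan's figures (ICC = 0).**
- N = 2 × 6.78² × (2.394 + 0.84)² / (1.5² × 0.689) = 620.3, rounded up to 621, as stated.
- Power = Φ(Δ/SE − 2.394), with SE = √[2 × 6.78² / (n × 0.689)].
- Main effect: SE = 0.344. At 1.2 mmHg, power is 86.2% (Table 1: 86.2%).
- Combined versus control: SE = 0.487. Power is 75.4% at 1.5 mmHg and 81.4% at 1.6 mmHg (Table 1: 75.3% and 81.3%).

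The arithmetic is right, and the tables assume full independence.

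**Adding within-group correlation.** The protocol gives neither group size nor ICC, so both are assumptions. Let m be the number analysed per group and DE = 1 + (m − 1) × ICC in the three active arms, with DE = 1 in usual care. The variance of a contrast is then multiplied by:
- main effect: (3·DE + 1)/4
- combined versus control: (DE + 1)/2

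Take m = 10, which is about 14.5 randomised per group × 0.689:

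| | ICC 0 | ICC 0.01 | ICC 0.02 |
|---|---|---|---|
| DE | 1 | 1.09 | 1.18 |
| Variance factor, main effect | 1 | 1.0675 | 1.135 |
| Variance factor, combined vs control | 1 | 1.045 | 1.09 |
| Power, main effect, 1.2 mmHg | 86.2% | 83.6% | 81.0% |
| Power, combined vs control, 1.5 mmHg | 75.3% | 73.2% | 71.1% |
| Power, combined vs control, 1.6 mmHg | 81.3% | 79.4% | 77.4% |
| N per arm for 80% at 1.5 mmHg, combined vs control | 621 | 649 | 677 |

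**False-positive rate of the planned tests.** Per test it is 2 × [1 − Φ(2.394/√factor)]. For a main effect this rises from 1.67% to 2.0% and 2.5%. For combined versus control it rises to 1.9% and 2.2%. Family-wise error over the three correlated contrasts, by simulation of the four arm means, is 4.1% at ICC 0, 4.9% at 0.01 and about 5.8% at 0.02.

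**Larger clusters.** With m = 25, ICC 0.01 to 0.02 gives main-effect power of 79.2% to 72.4% at 1.2 mmHg, and a per-test rate of 2.8% to 4.0%. If merging made each clinic-arm a single cluster, m would be 2250/4/9 × 0.689 ≈ 43. At ICC 0.01 that gives DE = 1.42, main-effect power of 74.0% and a per-test rate of 3.7%. That is an upper bound on cluster size.

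**What these ICCs mean.** The between-group SD is √ICC × 6.78, which is 0.68 mmHg at 0.01, 0.96 at 0.02 and 1.52 at 0.05. BACKGROUND AND RATIONALE gives 3–4 lb per mmHg, so ICC 0.01 corresponds to group-mean weight loss varying with an SD of 2.0–2.7 lb. ICC 0.05 would need 4.5–6.1 lb, against an expected maintained difference of 6–8 lb.

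**Hypertension endpoint (approximate).** Using the logrank formula and the HPT rate, power for the sodium contrast reproduces at 81.5% against 82.5% in Table 6. Applying the design effect to events with m = 10, it falls to 78.5% at ICC 0.01 and 75.6% at ICC 0.02. Weight loss stays above 99%.

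**The case against.** The strongest reply is that the size depends on two quantities the protocol does not state, and that nothing changes at ICC zero. That is correct. ICC 0.05 would lower the two headline powers to 73.2% (main effect, 1.2 mmHg) and 65.1% (combined versus control, 1.5 mmHg). But it implies a between-group SD as large as the 1.5 mmHg design difference, so it serves only as an upper illustration.

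A reader might infer that the family-wise 5% is simply not protected. The figures do not support that: at ICC 0.01 with 10 per group it is still 4.9%, because Bonferroni is slightly conservative for these correlated contrasts.

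A reader might also infer that Tables 1 to 4 overstate the power that the trial will have. That is not shown either. The protocol calls its 31.1% censoring conservative. DATA ANALYSES also puts baseline DBP in the model, which on the protocol's own components cuts the variance from 46.0 to 41.2. With that adjustment and ICC 0.02 (m = 10), power is 85.6% for the main effect at 1.2 mmHg and 76.5% for combined versus control at 1.5 mmHg, close to the stated 86.2% and 75.3%. These offsets can restore power. They do not correct the standard error.

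The nesting also loosens. Fixed Wt and WtNa groups last about 26 weeks (14 + 6 × 2), the endpoint is at 36 months, and cohorts are merged in between. This argues against relying on initial group alone. Merging stays within arm, though, so correlation can persist in larger clusters.

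Finally, a statistical analysis plan, not shown here, could add the missing term. It would repair the tests, but not the power printed in the protocol.

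**Conclusion.** The point stands in conditional form. The protocol treats three arms in groups and analyses everyone as independent. Under any positive within-group correlation the planned standard errors are too small, and Tables 1 to 4 are valid only for ICC = 0.

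At the assumed ICC of 0.01 to 0.02 with 10 analysed per group, the cost is about 2 to 5 points of power and up to about 0.8 of a percentage point of per-test error. Main effects at 1.5 mmHg have ample slack: 97.5% stated, still above 95% here. Combined versus control has little. It is already below 80% at 1.5 mmHg, and before any offset it drops below the claimed 80% at 1.6 mmHg.

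The direction is certain given positive correlation; the size is not. The change is worth making because it is cheap and group membership is hard to reconstruct later.

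**What to change.** - **Data:** record each active participant's intervention group (clinic × arm × cohort).
- **Primary DBP contrasts:** keep the factorial terms and baseline DBP, and add a random intercept for intervention group in Wt, Na and WtNa only. Treat usual-care participants as singletons and use small-sample degrees of freedom (Satterthwaite or Kenward-Roger).
- **Hypertension endpoints:** use group-clustered robust variance in the Cox model.
- **Sensitivity analysis:** because cohorts are merged within arm, repeat with clinic-by-arm as the cluster. This leaves only 27 active clusters (9 × 3), so the small-sample correction matters.
- **Power:** state that Tables 1 to 4 assume ICC = 0, and show power over a small range of ICC and group size.

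The cost is one data field and revised analysis wording, with no more participants or visits. Stated power becomes somewhat less favourable, and intervals widen slightly if the ICC is above zero. If it is near zero, results are essentially unchanged.

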Several strategies may be used to deal with the effects of such biases. The primary analysis will use the termination blood pressure as defined in Phase I of TOHP. This is the last recorded blood pressure prior to the initiation of

drug therapy. This includes blood pressures measured after becoming an endpoint according to the definition of SBP $_{\geq}140$ mmHg or DBP $_{\geq}90$ mmHg, but prior to starting medication. Because it is recognized that these latter measurements may be biased, secondary analyses will be performed to confirm the results of the primary analysis. These include an analysis of blood pressures taken at the time of diagnosis for those who become hypertensive, imputing minimum values of 90 mmHg for DBP and 140 mmHg for SBP for those who go on BP medications, and also a multivariate repeated measures analysis. The latter approach would use all measured blood pressures on an individual either including or excluding those following diagnosis. In this way, both the within-person variation as well as an effect of "self-intervention" could be taken into account.

Secondary endpoints in the trial, including changes in SBP and the development of diastolic and systolic hypertension, will also be examined. The former will be evaluated in the same manner as changes in DBP described above. For the hypertension endpoints, crude relative risks and a chi-square test will be calculated for each hypothesis to compare cumulative incidence rates over the duration of the study. We will compute Kaplan-Meier incidence-free survival curves and the logrank test statistic. A Cox proportional hazards regression analysis will be performed to adjust for potential confounders such as baseline BP, age, sex, and race.

Intermediate variables such as urinary sodium and body weight will be monitored on a regular basis and compared across intervention groups.

This trial will also provide the opportunity to explore any differential response to intervention by race, and gender, as well as body mass index,

waist to hip ratio, cigarette smoking habits, pulse rate, family history of hypertension, and baseline electrolyte excretion. Currently we expect to recruit a sample with approximately 21% blacks and 33% women. While power will not be adequate to test the effect of the interventions within these subgroups, we will explore any differences among them.

STUDY ADMINISTRATION

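### Randomisation is stratified by nine clinics, but clinic is named in none of the planned tests; adding it is a small, free gain in precision

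*Protocol*

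**What the plan says.** Study Design section: "All nine clinics will randomize participants into all four arms", with equal allocation to the four groups, and "Randomization will be stratified by clinic to insure even distributions into the four treatment groups at each of the clinical centers". Clinic is the only stratification factor that the protocol names.

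Data Analyses section, continuous endpoints: "The analysis of variance for a two-by-two factorial design will be used to test the main effects of weight loss and of sodium restriction". Two-group comparisons such as combined intervention versus control use a t-test, and also multiple regression. The regression covariates are introduced by way of example: "Multiple regression analyses will be performed to adjust for other covariates, such as age, sex, and initial weight and urinary sodium". Baseline pressure is a firm commitment: "mean initial DBP will also be included in the model". One reason given for including it is to reduce the error variance.

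Data Analyses section, hypertension endpoints: a chi-square test, Kaplan-Meier curves and the logrank statistic, none with strata. For the adjusted analysis, "A Cox proportional hazards regression analysis will be performed to adjust for potential confounders such as baseline BP, age, sex, and race". This list too is illustrative.

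**The concern.** When treatment is balanced within clinic by design, any variation in outcome between clinics cancels out of the treatment comparison. An analysis that omits clinic still counts that variation as error, so its standard error is larger than the true sampling variability of the estimate. Intervals come out slightly too wide, the test runs below its nominal level, and some power is lost.

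The protocol gives some reason to expect differences between clinics. Prescreening and recruitment procedures are left to each clinic, intervention starts at the clinic's discretion and is delivered mainly in groups, and blood pressure measurement is described as subjective. What is at stake is a little precision. It matters most for combined intervention versus usual care, where the Sample Size and Power section already concedes that 2250 participants fall short of 80% power at 1.5 mmHg for change to termination.

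**Working it through.** **Inputs from the protocol (Sample Size and Power).** SD of DBP change to termination 6.78 mmHg; 31.1% censored; three Bonferroni-adjusted comparisons, so the two-sided level is 0.05/3 = 0.0167 and z = 2.394; z for 80% power 0.84; total 2250, so 1125 per side for a main effect and 562.5 per side for combined versus control.

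**Assumed input.** The share f of the variance in DBP change that lies between clinics. The protocol gives no figure. The range used is 1% to 5%, with 10% as an outer case.

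**Step 1: reproduce the stated figures.**
- Sample size: N = 2 × 6.78² × (2.394 + 0.84)² / (1.5² × 0.689) = 620.3, so 621 per group and 2484 in total, as stated.
- Main effect at 1.2 mmHg: n = 1125 × 0.689 = 775.1 per side; SE = 6.78 × √(2/775.1) = 0.344; power = Φ(1.2/0.344 − 2.394) = 86.2%. Table 1 gives 86.2%.
- Combined versus control at 1.5 mmHg: n = 562.5 × 0.689 = 387.6 per side; SE = 6.78 × √(2/387.6) = 0.487; power = Φ(1.5/0.487 − 2.394) = 75.4%. Table 1 gives 75.3%.

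These calculations contain no clinic term, so the omission makes none of them wrong.

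**Step 2: the effect of omitting clinic.** Treat 6.78² as the total variance, including the clinic share. With balance within clinic, the true SE of the difference is SE × √(1 − f), while the analysis without clinic reports SE. Hence:
- SE overstatement = 1/√(1 − f) − 1
- true level = 2 × [1 − Φ(2.394/√(1 − f))]
- power without clinic = Φ[(Δ/SE − 2.394)/√(1 − f)]
- power with clinic = Φ[Δ/(SE × √(1 − f)) − 2.394]

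| f (assumed) | SE too large by | True level of a 0.0167 test | Main effect, 1.2 mmHg: without / with clinic | Combined vs control, 1.5 mmHg: without / with clinic |
|---|---|---|---|---|
| 1% | 0.5% | 0.0161 | 86.3% / 86.6% | 75.5% / 75.8% |
| 3% | 1.5% | 0.0151 | 86.6% / 87.4% | 75.7% / 76.8% |
| 5% | 2.6% | 0.0140 | 86.8% / 88.1% | 75.9% / 77.8% |
| 10% | 5.4% | 0.0116 | 87.5% / 90.0% | 76.5% / 80.3% |

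**Step 3: logrank test.** This was simulated with 9 clinics of 250, allocation balanced within clinic, a 43.5% control event rate over 3.5 years, the protocol's assumed risk reductions, and a normally distributed clinic effect on the log hazard. There were 3000 runs per setting, and the test was the sodium main effect at the 0.0167 level.
- Clinic SD 0.2 (assumed): level 0.013 unstratified, 0.014 stratified; power 81.0% and 81.6%.
- Clinic SD 0.4 (assumed): level 0.012 and 0.015; power 81.3% and 83.0%.

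Monte Carlo error is about 0.2 points on the level and 0.7 points on power, so the differences at SD 0.2 are within noise. At SD 0.4 the direction matches the linear case.

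**Step 4: cost.** Nine clinics take 8 degrees of freedom. About 2250 × 0.689 = 1550 participants are expected to have an uncensored termination measurement.

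**The case against.** The strongest reply is that silence is not exclusion. Both covariate lists are given by way of example, nothing says that clinic will be left out, and the exact covariate set is commonly settled in a statistical analysis plan, which is not at hand. The Study Administration section also gives the Design and Analysis Subcommittee responsibility for stratification and for proposing specific analyses. This stands for the multiple regression and Cox models. It does not cover the ANOVA, t-test, chi-square and logrank test, which are stated outright with no covariate list or strata.

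A second reply is that clinic effects on DBP change may be very small. Measurement is standardised and certified, random-zero devices are used, entry DBP is confined to 83–89 mmHg, the outcome is a change from baseline, and baseline DBP is in the model. That is fair. The clinic share is purely an assumption, and at 1% the loss is negligible. Differences between interventionists would also show mainly as treatment effects that vary by clinic, which a fixed clinic term does not address.

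A reader might infer more: that the standard errors and tests disregard the design so badly that the results are unsafe, or that false positives are inflated. The protocol does not support this. With balance within clinic the error runs the other way, and the estimated mean difference in DBP is unaffected. A reader might also infer that the time-to-event estimates are materially pulled toward no effect. The simulation examined the level and power of the logrank test, not the hazard ratio. It shows at most a modest loss of power at the larger assumed clinic effect, on endpoints that the protocol treats as secondary.

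**Conclusion.** The point holds as a minor improvement and is no threat to validity. The trial randomises within clinic, and the ANOVA, t-test, chi-square and logrank test are stated without it. If clinic explains 1% to 5% of the variance in DBP change, the loss is confined to mildly conservative tests. Power falls by about 0.3 to 1.3 points for a main effect at 1.2 mmHg, and by about 0.4 to 1.9 points for combined versus usual care at 1.5 mmHg. Even at 10% the latter loss is under 4 points. These sizes rest on the assumed clinic share, on close balance of arms within clinic, and on the protocol's own SD and censoring rate. If clinic does not predict the outcome, nothing is lost by omitting it and almost nothing by including it.

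**What to change.** In the Data Analyses section, name clinic (9 levels) as a fixed term, together with baseline DBP, in the primary linear model for the two main effects and in the model for combined intervention versus usual care. State that the logrank test and the Cox model are stratified by clinic. Naming these in advance also removes a later choice between results with and without clinic.

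Taking the combined-versus-usual-care comparison as a contrast from a single four-group model, in place of a two-group analysis, is optional. The protocol already plans regression for two-group comparisons, and clinic can be added there.

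The cost is a sentence or two of analysis wording and 8 degrees of freedom. No new data and no change to the sample size are needed.
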